### 3.5. Rationale for Study and Starting Dose

Given that pGSN is a naturally occurring plasma protein, the risk of drug toxicity related to rhu-pGSN infusion is expected to be low. In healthy primates dosed for 14 days, drug levels were similar to those obtained in human patients with pneumonia after administration of 12 mg/kg without evident toxicities. The doses given to humans have reached 24 mg/kg for 3 consecutive days. No distinctive safety signal was seen in the 2 small BioAegis studies to date; in fact, SAEs were numerically fewer in rhu-pGSN recipients compared to saline-placebo control subjects. However, in Study CBC-101 evaluating sick patients in the ICU administered a previous formulation of rhu-pGSN, 7 of 21 rhu-pGSN and 0 of 7 placebo recipients died ([Table 2](#)). None of the deaths were judged to be related to study drug and were all attributed to the serious underlying conditions of the participants. A post-hoc analysis indicated the rhu-pGSN group had higher acuity scores than the placebo group. All but one subject who died in Study CBC-101 were in the single-dose rhu-pGSN dosing groups.

Efficacy has only been demonstrated in animal models. It is anticipated that in sick patients, pGSN levels would be lower than normal at presentation and that rhu-pGSN administered IV would be consumed more rapidly than in healthy subjects. As such, efficacy in sick patients may require doses higher than used in the earlier clinical trials. Based on the previous human experience, 3 daily doses of 6, 12, and 24 mg/kg of rhu-pGSN were well tolerated in patients with CAP. An accelerated dosing schedule where rhu-pGSN was administered to patients hospitalized with COVID-19 pneumonia as 12 mg/kg at time 0, 12, and 36 hours was also generally well tolerated.

Before treating a larger number of critically ill patients to establish proof of concept in subjects with ALI/ARDS, the Sponsor aims to study the safety, tolerability, and PK of IV rhu-pGSN administered to healthy subjects. The current study is designed to primarily evaluate the safety and tolerability of sequential ascending doses of rhu-pGSN at 6, 12, 18, and 24 mg/kg of body weight, each given 5 times at 0, 12, 36, 60, and 84 hours.

A risk analysis of the immunogenicity potential of rhu-pGSN has been conducted. Overall, the risk assessment based upon product, process, and subject factors indicates a low potential for generation of an immune response. Anti-pGSN antibodies could in theory be clinically

meaningful. In the current study, specimens will be collected for ADA measurements at the first and last study visit.

## **4. STUDY OBJECTIVES AND ENDPOINTS**

### **4.1. Objectives**

#### **4.1.1. Primary Objective**

- To evaluate the safety and tolerability of 4 sequentially ascending doses of rhu-pGSN at 6 mg/kg, 12 mg/kg, 18 mg/kg, and 24 mg/kg of actual body weight administered by intravenous (IV) infusion for 5 doses at 0, 12, 36, 60, and 84 hours to healthy subjects

#### **4.1.2. Secondary Objectives**

- To characterize the pharmacokinetic (PK) profile of rhu-pGSN following administration of multiple (5) doses of rhu-pGSN to healthy subjects assigned to 4 dose levels (6, 12, 18, or 24 mg/kg)
- To investigate the development of anti-pGSN antibodies following administration of multiple (5) doses of rhu-pGSN administered to healthy subjects assigned to 4 dose levels (6, 12, 18, or 24 mg/kg)

## **4.2. Endpoints**

### **4.2.1. Primary Endpoint**

- Incidence and severity of AEs regardless of causality graded according to the Toxicity Grading Scale for Healthy Adult and Adolescent Volunteers Enrolled in Preventive Vaccine Clinical Trials

### **4.2.2. Secondary Endpoints**

- PK for IV rhu-pGSN including, but not limited to:  $C_{max}$ ,  $T_{max}$ ,  $T_{1/2}$ ,  $AUC_{0-8}$ , and additionally after Dose #5,  $AUC_{0-24}$ , and  $AUC_{inf}$  (levels measured on Day 1 within 30 minutes predose, and at 15 minutes and 1, 2, 4, 8, and 12 hours after Dose #1 and on Days 4 and 5 within 30 minutes predose, and at 15 minutes and 1, 2, 4, 8, 12, and 24 hours after Dose #5)
- Presence of anti-rhu-pGSN antibodies at Day 28

## 5. INVESTIGATIONAL PLAN

### 5.1. Overall Study Design

Study BTI-101 is a Phase 1, randomized, double-blind, placebo-controlled, dose escalation, parallel design study to evaluate the safety, tolerability, and PK of IV rhu-pGSN or saline placebo administered as 5 doses each of 6, 12, 18, or 24 mg/kg of body weight. Each of 4 dosing cohorts will include 8 subjects randomized 3:1 rhu-pGSN:placebo (6 rhu-pGSN subjects:2 placebo subjects). Subjects will be healthy adults 18-50 years of age.

Doses will be administered at 0 hours (Day 1), 12 hours (Day 1), 36 hours (Day 2), 60 hours (Day 3), and 84 hours (Day 4). Subjects will be kept in-house until after the last blood sample is taken on Day 5. Subjects will return for follow-up 7 days after the initiation of therapy (Day 7) and on Day 28 for the End-of-Study (EOS) Visit. After each cohort has completed the Day 7 visit, review of the safety results (including labs) will be conducted (and unblinded where appropriate) before the initiation of the next higher dose cohort.

To assess safety and tolerability, subjects will undergo physical examinations (including vital sign measurements), AE assessments, concomitant medication assessments, and safety laboratory testing. Blood samples will be collected for analysis of pGSN levels and antibodies against pGSN. See [Table 4](#) for a schedule of all study events.

### 5.2. Safety Review Committee

The safety data will be reviewed by a Safety Review Committee (SRC) comprised of at least 1 expert clinician, the Medical Monitor at the contract research organization, and the Sponsor's Chief Medical Officer.

Adverse events (AEs) will be categorized as "serious" according to the judgement of the site investigator as to whether the definition of SAE (section 9.1.2) is met and then reviewed and adjudicated by the SRC. The "severity" of an AE will be graded according to the Toxicity Grading Scale for Healthy Adult and Adolescent Volunteers Enrolled in Preventive Vaccine Clinical Trials. An individual patient will be discontinued permanently from study treatment if they experience any serious adverse event (SAE) or a severity Grade 3 or greater AE (including infusion reactions). Further study treatment and enrollment will be paused pending review by the SRC if there are two Grade 3 AEs, one Grade 4 AE, or one SAE. The study will only be resumed if the SRC unanimously judges the AEs as unrelated to study treatment and procedures after consultation with regulatory and outside experts as needed.

The SRC will review safety data (including lab tests) through the Day 7 visit for each dosing arm to determine if it is safe to initiate the next cohort according to the safety criteria for stopping doses ([Section 5.3](#)).

### 5.3. Safety Criteria for Stopping Doses

Dosing of rhu-pGSN may be stopped during the study at the discretion of the SRC. All AEs occurring during this healthy-volunteer study will be presumed to be related to study drug unless occurring before the study therapy is initiated pending review by the SRC.

An individual patient will be discontinued permanently from study treatment if they experience any serious adverse event (SAE) or a severity Grade 3 or greater AE (including infusion-related reactions) regardless of causality.

Further study treatment and enrollment will be paused pending review by the SRC if any patient dies or there are two Grade 3 AEs, one Grade 4 AE, or one SAE. The study will only be resumed if the SRC unanimously judges the death or AEs as unrelated to study treatment and procedures after consultation with regulatory and outside experts as needed.

### **5.3.1. Management of rhu-pGSN Infusion-Related Reactions**

In general, doses should only be temporarily interrupted for Grade 1 or 2 AEs, but treatment to control symptoms should be provided, if applicable. The infusion can be restarted at a slower rate once symptoms have dissipated. If symptoms recur, the infusion will be permanently discontinued. If a subject develops a Grade 3-4 IRR:

- The infusion should be stopped immediately, and the infusion tubing should be disconnected from the subject.
- The subject should receive appropriate treatment with an antihistamine and/or acetaminophen (paracetamol) and/or methylprednisolone (or equivalent) and, if necessary, further medications (i.e., epinephrine, bronchodilator).
- The subject may not receive further infusions of study therapy.

### **5.4. Duration of Subject Participation**

The duration of subject participation includes screening for up to 6 weeks, study treatment for 4 days, and safety follow-up through 28 days post-first dose for a maximum duration of subject participation of 10 weeks.

### **5.5. End of Study Definition**

End of study (EOS) will be defined as the date the last subject completes the EOS Visit. The Sponsor will notify all applicable regulatory agencies in accordance with local requirements when the study has ended.

### **5.6. Criteria for Treatment Discontinuation**

Subjects are free to discontinue their participation in the study at any time and without prejudice to further treatment. The Investigator must withdraw any subject from the study if that subject requests to be withdrawn, or if it is determined that continuing in the study would result in a significant safety risk to the subject.

The subject's participation in this study may be discontinued for the following reasons:

- Any SAE
- Grade 3 AEs or Grade 4 AE
- Subject withdrew consent
- Subject is unwilling or unable to continue the study or is lost to follow up
- Subject is non-compliant with study procedures/study protocol

- Investigator decides that withdrawal from the study is in the best interest of the subject
- Any clinically significant change in subject's medical condition (at the discretion of the Investigator)
- Sponsor decision to end the study

If a subject withdraws from the study prematurely, assessments scheduled for the EOS Visit should be performed as soon as possible. If a subject refuses further assessment, the subject should be contacted for safety evaluations (AE/concomitant medications/potential pregnancy) approximately 28 days after study withdrawal.

If such withdrawal occurs, or if the subject refuses to participate in the EOS Visit, the Investigator must determine the primary reason for a subject's withdrawal from the study and record the information on the electronic case report form (eCRF). If the reason for withdrawal is an AE, monitoring should continue until the outcome is evident. The specific event or test result(s) must be recorded in the eCRF. At the discretion of the Sponsor, subjects may also be removed from the study ([Section 5.4](#)).

It should be clearly documented in the source data whether a subject withdrew his/her consent and will not enter the follow-up phase, or if a subject withdrew his/her consent for study drug treatment but will continue further participation in the study.

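### Section 5.6 lets an SAE or a Grade 3 or 4 AE end study participation where Sections 5.2 and 5.3 end only treatment, so Day 7 and Day 28 data can be cut short in those subjects

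*Combined protocol and SAP*

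**What the plan says.** Section 5.3, with Section 5.2 to the same effect, says of a subject with an SAE or an AE of Grade 3 or higher: "An individual patient will be discontinued permanently from study treatment". Neither section says anything about leaving the study.

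Section 5.6 is headed Criteria for Treatment Discontinuation, but its list opens with "The subject's participation in this study may be discontinued for the following reasons". The first two entries are any SAE and Grade 3 or Grade 4 AEs. For a subject who leaves, it then provides:

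- Early assessments: "If a subject withdraws from the study prematurely, assessments scheduled for the EOS Visit should be performed as soon as possible".
- A later contact, about 28 days after withdrawal, with a condition attached: "If a subject refuses further assessment, the subject should be contacted for safety evaluations".
- Follow-up of the event that caused the withdrawal: "If the reason for withdrawal is an AE, monitoring should continue until the outcome is evident".
- A record of whether the subject left altogether or "if a subject withdrew his/her consent for study drug treatment but will continue further participation in the study". This is the only place where Section 5.6 separates the two, and it concerns withdrawn consent.

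Section 9.7 requires AEs to be recorded until 28 days after the last dose. It also says that after the EOS Visit only new treatment-related SAEs need be captured, and it ends follow-up of other AEs at the EOS Visit if that comes first. Section 10.3 keeps every dosed subject in the full analysis set and rules out imputation.

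**The concern.** Safety is the primary objective, and each dose level has six active subjects. After screening, Table 4 schedules safety labs only on Day 7 and Day 28, and antibody sampling only on Day 1 and Day 28. Few assessments remain if a subject leaves early.

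The sections leave open whether a subject taken off drug for an SAE or a Grade 3 or 4 AE stays on that schedule. If such a subject is withdrawn from the study, one early assessment can stand in for both later visits. Late AEs, labs and the antibody result would then be missing because of a safety event, in the subjects whose later course is of most interest, and nothing is imputed. The Safety Review Committee (SRC), which decides on escalation from data through the Day 7 visit, could lack that subject's Day 7 labs.

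**Working it through.** **1. The provisions side by side**

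| Question | Sections 5.2 and 5.3 | Section 5.6 | Section 9.7 |
|---|---|---|---|
| What ends after an SAE or Grade 3+ AE? | Treatment, mandatory | Participation, permitted | Not addressed |
| Does the subject stay for Day 7 and Day 28? | Not stated | Not stated; EOS assessments brought forward on withdrawal | Not stated |
| Are new AEs collected after early EOS assessments? | Not stated | Contact at about 28 days, written only for subjects who refuse assessment | To 28 days after last dose, but after the EOS Visit only treatment-related SAEs |
| How long is the causal AE followed? | Not stated | Until its outcome is evident | To the EOS Visit at the latest, except treatment-related SAEs |

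**2. What follows for one subject (assumed timing)**

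Suppose a subject has a Grade 3 AE after Dose 2 on Day 1, is withdrawn on Day 2, and cooperates.

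- The early assessment falls 7 − 2 = 5 days before Day 7 and 28 − 2 = 26 days before Day 28.
- The causal AE is monitored to its outcome under Section 5.6.
- No later contact for new AEs is written, because the subject did not refuse assessment.
- If the early assessment counts as the EOS Visit, which the protocol does not settle, Section 9.7 then asks only for new treatment-related SAEs.
- The antibody sample is taken one day after first exposure, too early to stand for the Day 28 endpoint in Section 4.2.2. Section 3.5 describes the second antibody specimen as taken at the last study visit, so the early sample could even be filed as that result.

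After Dose 5 the treatment stop has nothing left to act on, but Section 5.6 still allows participation to end.

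**3. Size, as an illustration**

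Inputs from the protocol: n = 6 active subjects per dose level and 24 in all; 90% detection probability and a 32% rate for n = 6 (Section 10.2, Table 5). The number lacking late follow-up is an assumption (1 to 3).

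The plan's own figure comes first: P(at least one AE) = 1 − (1 − p)^n = 1 − 0.68^6 = 90.1%, which agrees with Table 5. The zero-event 90% upper limit is 1 − 0.1^(1/6) = 31.9%, also in agreement.

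For a late event type that could only be seen in subjects still followed:

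| Followed at a dose level | P(at least one) at 32% | Zero-event 90% upper limit |
|---|---|---|
| 6 | 90.1% | 31.9% |
| 5 | 85.5% | 36.9% |
| 4 | 78.6% | 43.8% |
| 3 | 68.6% | 53.6% |

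Pooled over 24 active subjects, the limit moves from 9.15% to 9.53% with one lost and to 10.38% with three lost.

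For antibodies, Section 10.4.3 promises 95% intervals without naming a method. Assuming exact two-sided (Clopper–Pearson) limits, the upper limit with no positives is 1 − 0.025^(1/6) = 45.9% for six results and 1 − 0.025^(1/5) = 52.2% for five.

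**The case against.** The strongest reply is that nobody is dropped from safety follow-up. Section 5.6 is permissive. It requires EOS assessments on leaving, and it follows an AE that caused withdrawal until the outcome is evident. Section 9.7 sets a recording window of 28 days after the last dose with no stated exception for early stoppers, and follows treatment-related SAEs beyond EOS. An SAE or a Grade 4 AE also pauses the study, so the SRC sees that event at once. All of this stands. A reader might infer that these subjects vanish from follow-up; the documents do not support that. The gaps that remain are the contact written only for refusers, the narrower capture after the EOS Visit, and the Day 7 and Day 28 labs and antibody sample.

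A reader might also infer that the primary endpoint is biased because the subjects with events are removed. That goes too far. The primary endpoint covers AEs of every grade, the triggering event is already recorded and graded, and Section 10.3 keeps the subject in the full analysis set. The dose group does not shrink from six to five, and the zero-event limits above cannot apply to the triggering type of event. Nor would the chance of a qualifying event among the 24 active subjects measure the problem: it is a probability of an event, not of withdrawal or lost data.

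Finally, the mandatory wording in Section 5.3 and the permissive wording in Section 5.6 need not conflict, since drug can stop while leaving stays optional. That reading is reasonable, but the heading of Section 5.6 works against it, and no section says what happens to the visits.

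**Conclusion.** The point holds in a limited form. The protocol mixes stopping treatment with leaving the study for SAEs and Grade 3 or 4 AEs, and does not say that subjects stopped for these events stay on the Day 7 and Day 28 schedule. The loss is confined to later or different AEs, scheduled labs and the antibody result.

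The effect on one dose level is modest if one subject is affected (85.5% instead of 90.1% detection at a 32% rate) and grows quickly with more; pooled over all doses it is small. These figures assume the number lost, a late event type not yet seen, and the same late-event risk in the subjects lost as in the others. If subjects with a serious or severe event are more prone to later ones, the loss is greater; the documents give nothing from which to estimate that. The change is worth making because it is cheap and protects data the plan already intends to collect.

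**What to change.** - Reconcile Sections 5.2 and 5.3 with Section 5.6. Which stopping or withdrawal rule applies is for the sponsor to decide.
- In Section 5.6, list reasons for stopping study drug separately from reasons for leaving the study. The existing safety-risk and best-interest grounds for withdrawal should not be lost in the process.
- State that a subject whose drug is stopped for an AE remains, with consent and unless withdrawn on a ground the protocol keeps, on the scheduled Day 7 and Day 28 safety, laboratory and antibody assessments.
- Align Section 5.6 with Section 9.7, so that an early EOS assessment does not end AE collection before 28 days after the last dose, and so that the two agree on how long an AE is followed.

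The cost is protocol wording. No visits are added: Day 7 and Day 28 are already in Table 4, whose footnote allows AE interviews by phone.

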## **9.7. Reporting Adverse Events**

All AEs, serious and nonserious, will be fully documented on the appropriate eCRF. For each AE, the Investigator must provide its duration (start and end dates or ongoing), intensity,

assessment of causality and whether specific action or therapy was required. All AEs occurring during this healthy-volunteer study will be presumed to be related to study drug unless occurring before the study therapy is initiated pending review by the SRC.

All AEs that occur from the signing of the informed consent form (ICF) until the first dose of study drug should be recorded on the AE eCRF page only if the event was related to a study procedure. All other AEs/findings prior to the first dose of study drug should be recorded as medical history on the applicable eCRF page. All AEs occurring from the first dose of study drug until 28 days after the last dose of study drug must be recorded on the AE eCRF.

All SAEs and Grade 4 AEs must be reported to the Sponsor within 24 hours of the Investigator's knowledge. All AEs occurring during this healthy-volunteer study will be presumed to be related to study drug unless occurring before the study therapy is initiated pending review by the SRC. This reporting should be done by faxing/emailing the completed SAE Report Form to the number provided on the SAE Report Form. After the EOS Visit, only new treatment-related SAEs need to be captured on the AE eCRF and reported to the Sponsor.

Investigators must follow subjects with AEs/SAEs until the event has resolved, the condition has stabilized, withdrawal of consent, the subject is lost to follow up or death OR until the EOS Visit, whichever occurs first. New and ongoing treatment-related SAEs should be followed beyond the EOS Visit. If the subject dies, this should be captured as the outcome of the AE unless no link between the AE and the subject death can be established, in which case the AE will be marked as ongoing and the death will be reported as a separate event.

If a subject is lost to follow up, this should be captured accordingly within the AE eCRF and on the follow up SAE report.

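### Subjects who leave early and cooperate have no scheduled contact to collect new non-serious AEs, whereas those who refuse assessment do (Sections 5.6 and 9.7)

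*Combined protocol and SAP*

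**What the plan says.** Section 5.6 (Criteria for Treatment Discontinuation) has two rules for a subject who leaves the study early.

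- For the subject who cooperates: "If a subject withdraws from the study prematurely, assessments scheduled for the EOS Visit should be performed as soon as possible". No later contact is scheduled.
- For the subject who does not: "If a subject refuses further assessment, the subject should be contacted for safety evaluations". The contact covers AEs, concomitant medications and possible pregnancy, and is timed "approximately 28 days after study withdrawal".

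Section 9.7 (Reporting Adverse Events) sets the recording period: "All AEs occurring from the first dose of study drug until 28 days after the last dose of study drug must be recorded". It makes no exception for withdrawn subjects. The same section then narrows capture: "After the EOS Visit, only new treatment-related SAEs need to be captured on the AE eCRF and reported to the Sponsor". Follow-up of events already open runs to resolution or another listed end point "OR until the EOS Visit, whichever occurs first", with one exception: "New and ongoing treatment-related SAEs should be followed beyond the EOS Visit".

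Section 9.1.2 requires all SAEs up to 28 days after treatment stops to be recorded, related or not. Section 5.6 keeps an AE that led to withdrawal under monitoring until its outcome is known. It also recognises subjects who give up study drug but remain in the study.

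The EOS Visit is scheduled at 28 ± 3 days after Dose #1 (Section 8 and Table 4). Table 4 has one EOS column and no early-termination visit.

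**The concern.** AEs in this study are found by interview on fixed days (Table 4, footnote e): daily for five days, then at Day 7 and Day 28. A subject who withdraws from the study and accepts the early assessments appears to leave that interview schedule, and nothing replaces it. A subject who refuses assessment is still asked about AEs some four weeks later. The plan therefore arranges longer AE coverage for the subjects who are harder to reach than for those who are easier to reach, and gives no reason.

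Incidence and severity of AEs is the primary endpoint (Section 4.2.1). Anyone given part of one dose is in the full analysis set, missing data are not imputed (Section 10.3), and AEs are reported as counts and proportions of subjects (Section 10.4.1). A subject whose later weeks are not asked about stays in the denominator, and those weeks are in effect treated as free of new events. With 6 active subjects per dose level, one subject is 1/6 = 17% of a cohort.

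**Working it through.** The plan states no figure on this point, so there is nothing to reproduce. The check compares the rules and does date arithmetic.

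**Inputs.** Doses at 0, 12, 36, 60 and 84 h (Section 7.4). AE recording until 28 days after the last dose (Section 9.7). EOS Visit at 28 ± 3 days after Dose #1 (Section 8). Contact with a refuser about 28 days after withdrawal (Section 5.6). The plan gives neither a dropout rate nor a timing for the early assessments beyond as soon as possible, so their delay after the last dose, d days, is an assumption.

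**Step 1: end of the required window.** Days after Dose #1 = (time of last dose in hours)/24 + 28.

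| Last dose received | Hours/24 | Window ends (days after Dose #1) |
|---|---|---|
| #1 | 0 | 28.0 |
| #2 | 0.5 | 28.5 |
| #3 | 1.5 | 29.5 |
| #4 | 2.5 | 30.5 |
| #5 | 3.5 | 31.5 |

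**Step 2: cooperative leaver.** Time in the window with no scheduled contact = 28 − d.

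- d = 1: 27 days. d = 7: 21 days. d = 14: 14 days.
- Illustration: the last dose is #3 and the assessments are done 2 to 3 days after Dose #1, so d = 0.5 to 1.5. Remaining time is 29.5 − 3 = 26.5 to 29.5 − 2 = 27.5 days. As a share of the whole window this is 26.5/29.5 = 90% to 27.5/29.5 = 93%. Withdrawal later after the last dose leaves less.

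**Step 3: refuser.** Withdrawal at time w cannot precede the last dose at time t, so w + 28 ≥ t + 28. The contact falls at or after the end of the window (subject to the word approximately) and can cover all of it.

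**Step 4: subject who completes the schedule, for scale.** The window ends at 31.5 days. An EOS Visit at 25, 28 or 31 days leaves 6.5, 3.5 or 0.5 days. That is a separate and much smaller shortfall.

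**Step 5: the two readings of Sections 5.6 and 9.7.**

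- *The early assessments are the EOS Visit.* Section 9.7 then asks only for new treatment-related SAEs afterwards. New non-serious AEs fall outside capture, although the same section requires all AEs for 28 days after the last dose.
- *They are not the EOS Visit.* The duty to record all AEs continues, but no contact is scheduled to carry it out. Recording depends on the subject reporting unprompted.

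Either way, new non-serious AEs in a cooperative leaver have no scheduled collection for 28 − d days.

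**The case against.** A reader might infer that bringing the EOS assessments forward closes AE capture at once, and that AEs after early withdrawal go uncollected. The documents do not support either statement.

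- Section 5.6 advances the assessments planned for the EOS Visit. It does not call them the EOS Visit, which is defined by time (28 ± 3 days after Dose #1). Section 9.7 still requires all AEs to be recorded for 28 days after the last dose.
- SAEs up to 28 days after stopping treatment must be recorded regardless of relatedness (Section 9.1.2). Treatment-related SAEs stay open after EOS, and post-dose AEs are presumed related pending committee review. An AE that caused withdrawal is monitored to its outcome.
- Sections 5.2 and 5.3 take subjects with an SAE or a Grade 3 or higher AE off study treatment, not out of the study. Section 5.6 says only that participation may end. Those who stay keep the Day 7 and Day 28 interviews.
- A subject who leaves because of an AE already counts as having an AE. Only further AE types or higher grades could be missed, so a shift towards a cleaner safety profile is not shown.
- Pregnancy is partly handled: subjects are to report one within 3 months of the last dose (Section 6.4), and outcomes are followed after discontinuation (Section 9.5).
- Dosing lasts 84 hours with subjects in-house to Day 5, and Section 10.3 expects nearly identical analysis sets, so early leavers may be few.

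All of this stands, and it confines the point to new non-serious AEs. It does not remove the point, because none of these provisions schedules a contact with a cooperative subject who has left the study. Two of them also sit badly with Section 9.7: all SAEs for 28 days against only treatment-related SAEs after EOS, and monitoring to outcome against follow-up ending at EOS.

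**Conclusion.** The point holds in a limited form. Section 5.6 gives the 28-day safety contact only to subjects who refuse assessment. Cooperative subjects who withdraw from the study have no scheduled collection of new non-serious AEs for 28 − d days of the period that Section 9.7 itself requires. The protocol also leaves open whether the early assessments trigger the EOS cut-off.

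The length of the gap rests on the assumed d, and the 90% to 93% figure belongs to one constructed case (last dose #3, assessments 2 to 3 days after Dose #1). The effect on the primary endpoint depends on how many subjects leave early, which the documents do not give. Neither its size nor its direction is shown, and no sample-size figure changes. This is an inexpensive improvement in AE ascertainment and a needed clarification. It is not a flaw that by itself undermines the safety conclusions.

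**What to change.** - **Section 5.6:** extend the existing safety contact (AEs, concomitant medications, pregnancy) to every subject who withdraws from the study early and has not refused contact. Time it no earlier than 28 days after the last dose.
- **Section 9.7:** state that an early-termination assessment is not the EOS Visit that ends AE capture, so that for these subjects capture of all AEs runs to the safety contact.
- **Sections 5.6, 9.1.2 and 9.7:** reconcile the recording and follow-up periods for AEs and SAEs so that they agree for subjects who leave early.

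The cost is a short amendment and one phone call per early leaver, with no added visits, samples or subjects.
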